3.3 Randomization

Patients enrolled in the study will be randomized following creation of the new upper extremity native fistula. Randomization will be performed post-operatively in order to avoid randomization of patients for whom a planned fistula does not actually get created. Randomization will be performed via the Internet using a web browser following verification of eligibility by the Data Coordinating Center.

Randomization will be based on a 1:1 study drug: placebo distribution. The random treatment assignment will be stratified by Clinical Center and by location of AV fistula (forearm versus upper arm). Stratification by Clinical Center is necessary because of possible regional differences in clinical practices. Within a Clinical Center, the predominant variables affecting outcomes will be related to the vascular surgeon placing the access. However, because of the large number of surgeons likely to be creating fistulae in each Clinical Center, it is impractical to stratify by surgeon. Stratification by location of fistula is necessary because of differences in

failure rates between forearm and upper arm fistulae. Treatment assignment codes will be made using random permuted blocks within each stratum.

3.4 Blinding

Treatment assignment will be masked to both patients and study personnel. Matching clopidogrel and placebo will be provided by Bristol-Myers Squibb and Sanofi-Synthelabo. One potential source of unblinding is prolonged hemostasis time after removal of dialysis needles at the termination of dialysis. Although it is possible that clopidogrel may prolong bleeding time and result in difficulty achieving hemostasis after removing dialysis needles, this should be an issue in only the subset of patients already receiving hemodialysis prior to enrollment in the study. Based on the demonstration that clopidogrel did not prolong the time to hemostasis in a group of nine hemodialysis patients⁴⁵, we do not expect inadvertent unblinding due to such events.

We anticipate that unblinding may be required in the following two circumstances: 1) prior to the performance of emergency surgery, and 2) if there is life-threatening hemorrhage where the transfusion of platelets to reverse the antiplatelet effects of therapy is indicated. When it is absolutely necessary that a study medication code be released, the Data Coordinating Center will reveal the medication for a given patient to the study nephrologist at the facility. After unblinding, the patient should be continued in the trial on study medication if possible. Given the short duration of study drug administration, we anticipate that the number of patients requiring unblinding will be small.

4. STUDY TREATMENT PLAN

4.1 Study Visits and Patient Contacts

Patients will be evaluated at three study visits. See Section 5 for details regarding the data collected at each visit. The first study visit will be a screening evaluation, during which eligibility will be assessed, and informed consent and baseline demographic/laboratory data will be obtained, and quality of life will be measured. It is preferred that this visit occur prior to creation of the new native fistula; however, enrollment will be permitted up to one calendar day following fistula creation. Randomization for treatment assignment will be performed following fistula creation surgery after verification that a fistula was created. If the surgeon reports that the fistula thrombosed in the operating room or in the recovery room, the patient should not be randomized. Randomization and study drug delivery to the patient must occur such that study drug administration can begin within one calendar day following fistula creation surgery. Contact will be made either in person or by telephone on the first working day following fistula creation surgery to verify that the patient has started the study medication and to remind the patient to take the medication as directed. During this contact, the study coordinator or investigator will ensure that the patient knows how to contact study personnel if questions arise or in the event of adverse events. If a patient is not randomized because of failure to create a native fistula, the patient will be informed that he/she will not be participating in the study.

The second study visit will occur six weeks after fistula creation (coinciding with completion of study drug). At this visit the patency of the fistula will be determined by physical examination (i.e., presence of bruit). Adverse events and side effects of treatment will be reviewed. Study drug pill count will be performed. A quality of life questionnaire will be completed⁴⁶⁻⁴⁷.

After the six-week study visit, additional data will be collected until the fistula suitability outcome is ascertained. The data will be collected through contacts with study subjects, their physicians, their dialysis units, and other sources as needed.

The third study visit will occur following ascertainment of the fistula suitability outcome. At this visit, a quality of life questionnaire will be completed⁴⁶⁻⁴⁷, procedures performed on the fistula will be documented, and adverse events will be reviewed. The patient will be informed that participation in the study has ended. Ascertainment of fistula suitability will occur during the fourth month following fistula creation for patients who are on dialysis within 4 months of fistula creation or during the first month of dialysis for patients who start dialysis > 4 months following fistula creation. The fistula suitability outcome will not be ascertained for those patients who do not start hemodialysis during the study period. If the fistula has not been used at the time of the suitability assessment, but may be used in the future, the patients will continue to be followed until it is determined whether the fistula is actually used.

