2.2 Design

The trial is a randomized, double-blind, placebo-controlled multi-center trial with a parallel treatment design. Patients with chronic renal failure who are on chronic hemodialysis or anticipated to begin chronic hemodialysis within 6 months will be randomized within one calendar day following creation of a new upper extremity native AV fistula to receive either clopidogrel or placebo for six weeks. Randomization will be on a 1:1 active drug:placebo allocation, and will be stratified by Clinical Center and location of AV fistula (forearm vs upper arm). Both patients and study personnel will be masked to treatment assignment. The sample size is 1284 patients, to be recruited at seven Clinical Centers over a 4-year period. Study drug administration will begin within one calendar day following native AV fistula creation and continue for 6 weeks following surgery. The primary outcome measure is fistula patency at the end of the 6-week study drug administration period. A secondary outcome measure is fistula suitability for dialysis.

A follow-up evaluation will be conducted six weeks following creation of the AV fistula. Fistula patency (primary outcome) will be ascertained at that visit. Contact will be made with the patient and/or dialysis unit on a monthly basis thereafter to obtain data related to the fistula suitability for dialysis outcome. All randomized patients who undergo creation of a native fistula will be followed regardless of whether or not they remain on their assigned treatments. Participation in the study will end once the fistula suitability outcome has been ascertained. Fistula suitability outcome ascertainment will occur during the fourth month following fistula creation for those patients who are either on chronic hemodialysis at the time of fistula creation or begin hemodialysis within 4 months of fistula creation. If dialysis is not initiated within 4 months of fistula creation, ascertainment of fistula suitability for dialysis will occur during the first month

of hemodialysis. If the fistula has not been used at the time of the suitability assessment, but may be used in the future, the patients will continue to be followed until it is determined whether the fistula is actually used.

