4.5 Study Completion

Participation in the study will end once the fistula suitability for dialysis outcome has been ascertained. This ascertainment will be completed by 150-180 days after fistula creation for patients already on chronic dialysis at the time of fistula creation and for patients who begin chronic dialysis within 120 days after fistula creation. For patients who start chronic dialysis >120 days following creation of the AV fistula, ascertainment of fistula suitability for dialysis will be completed by 30-60 days after the start of chronic dialysis. However, if the fistula has not been used at the time of the suitability assessment, but may be used in the future, the patients will continue to be followed until it is determined whether the fistula is actually used. For patients who do not start hemodialysis by the end of the study period, the fistula suitability outcome will not be ascertained and completion of study participation will coincide with the end of the study.

If fistula thrombosis occurs prior to the ascertainment of fistula suitability for dialysis, and if fistula patency is not restored, study participation will end at the time of fistula thrombosis or 30 days after study drug discontinuation, whichever comes later. Fistula thrombosis must be confirmed by a member of the study team or the patient's vascular surgeon. If fistula thrombosis occurs prior to the ascertainment of fistula suitability for dialysis, and if fistula patency is restored, participation in the study will end once the fistula suitability for dialysis outcome has been ascertained.

Data collection after study participation has ended will include hospitalization and mortality data obtained from national databases while the study is on-going and for up to five years after the study has ended.

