5.4 Follow-up Data

After the six-week study visit, contact will be made by the study coordinator with study subjects, their physicians, their dialysis units, and other sources on a monthly basis to capture data on interim events and to ascertain secondary outcomes. The data to be collected include:

1. Date of first cannulation of fistula.
2. Date at which fistula is used for four weeks of consecutive dialysis treatments.
3. Minimum dialysis machine blood flow rate during the 12 dialysis sessions prior to study completion. The minimum blood flow rate should be determined from the blood flow measurements recorded after the first hour and before the last 15 minutes of the dialysis session. Study completion will occur 5 months after fistula creation for patients who are on dialysis at the time of fistula creation or start dialysis within 4 months of fistula creation. Study completion will occur 4 weeks after dialysis initiation for patients who start dialysis >4 months after fistula creation. However, if the fistula has not been used at the time of the suitability assessment, but may be used in the future, the patients will continue to be followed until it is determined whether the fistula is actually used.
4. Procedures performed on fistula (fistulogram, angioplasty, thrombectomy, conversion to graft, ligation of draining veins), and dates of such procedures.
5. For patients not on chronic dialysis prior to creation of the fistula – date of first dialysis.
6. Intercurrent/Adverse Events - bleeding events and hospitalizations during the 30 days following end of study drug administration period. Death during the period of study participation.
7. Quality of life

For patients with fistula thrombosis and no restoration of patency during the six-week study drug administration period, quality of life data is collected as indicated in item 7.

Data collection after study participation has ended will include hospitalization data and mortality data obtained from national databases while the study is on-going and for up to five years after the study has ended.

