8. STATISTICAL DESIGN

8.1 Sample Size Calculations

From review of the literature, it is estimated that fistula thrombosis at 6 weeks (primary outcome) will occur in 25% of patients treated with placebo and failure to achieve fistula suitability for dialysis (secondary outcome) will occur in 40% of patients treated with placebo^{14, 28-35, 48}. In order to detect a 30% reduction in fistula thrombosis rate with 85% power and a 2 sided-alpha level of 0.05, 1284 patients are required (642 in each treatment group) assuming a 5% loss to follow-up rate, a 3% treatment drop-in rate, and a 3% treatment drop-out rate. This sample size also includes a slight (2.7%) upward adjustment to account for the O'Brien-Fleming stopping rule suggested by the Steering Committee. Under a fixed sample size design, the sample size of 1,284 would provide approximately 80% power to detect a 20% reduction in failure to achieve fistula suitability for dialysis.

Addendum: As of June 1, 2004 the recruitment period of the study was extended from 48 to 51 months based on the recommendation of the Data Safety and Monitoring Board (External Advisory Committee).

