8.2.2.2 Outcome Measures

Primary Analysis of Fistula Patency at 6 Weeks

The primary analysis will evaluate the effect of randomization to clopidogrel vs. placebo on the probability that a new fistula will be patent six weeks after randomization. This analysis will be carried out by applying the Mantel-Haenszel test to compare the proportion of patent fistulas at six weeks with stratification for Clinical Center and the location of the fistula. The comparison of the clopidogrel and placebo interventions in the primary analysis will be carried out using an intent-to-treat strategy in which patients are retained in their randomized groups regardless of their compliance to the treatments. A 2-sided hypothesis test will be conducted at the 5% level of significance.

Analyses of Secondary Outcomes

The Mantel-Haenszel test (with stratification for Clinical Center and fistula location) will also be used to evaluate the effect of randomization to clopidogrel on the two main secondary outcomes:

- a. the proportion of fistulae suitable for dialysis with or without radiological or surgical modification in the two treatment groups (secondary outcome measure).
- b. the proportion of fistulae suitable for dialysis without radiological or surgical modification in the two treatment groups (secondary outcome measure).

Other Secondary Analyses

Secondary analyses will include an analysis of the three outcome measures for patients in whom study drug is not deliberately discontinued during the six week study drug administration period. Study outcomes will also be analyzed using logistic regression and adjusting for additional covariates found by interactive data analysis to be predictive of the primary or secondary outcomes. Death rates in active drug and placebo groups will also be compared.

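### Entry into the fistula-suitability comparison depends on thrombosis, which the drug targets, and the stated 80% power allows nothing for patients who never start dialysis

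*Protocol*

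**What the plan says.** Patients not yet on dialysis are eligible if hemodialysis is expected within six months (Protocol 3.1, inclusion criterion 3). Their share of the sample is not given.

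On non-starters, Protocol 4.1 says: "The fistula suitability outcome will not be ascertained for those patients who do not start hemodialysis during the study period". Section 4.5 repeats the rule and adds that these patients stay in the study until it ends.

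On lost fistulae, 4.5 says: "if fistula patency is not restored, study participation will end at the time of fistula thrombosis or 30 days after study drug discontinuation", taking the later of the two. For thrombosis in the first six weeks, 4.4.4 (item 6) and 4.4.6 give 30 days after study drug is stopped. For those early losses, the closing paragraph of 5.4 names only quality of life for collection; the date of first dialysis (item 5) is not mentioned.

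Section 7.1 defines suitability through blood flow at dialysis sessions and does not say how a permanently lost fistula is classed. Section 8.2.2.2 compares proportions suitable with a Mantel-Haenszel test, names no denominator, and declares intent-to-treat for the primary analysis only.

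On power, 8.1 says that under a fixed design "the sample size of 1,284 would provide approximately 80% power to detect a 20% reduction in failure to achieve fistula suitability for dialysis". On deaths, 8.2.2.2 says: "Death rates in active drug and placebo groups will also be compared". Item 6 of 5.4 lists "Death during the period of study participation", while 4.5 and 5.4 also plan mortality data from national databases after participation ends.

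**The concern.** Two rules meet in the pre-dialysis patient. With a patent fistula, the patient is followed until dialysis starts or the study closes, and enters the suitability comparison only if dialysis starts. With an unrestored thrombosis, follow-up stops early and dialysis start is no longer recorded. A single rule based on dialysis start therefore cannot be applied to both kinds of patient.

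Thrombosis is the event clopidogrel is meant to prevent, so the set of patients compared is itself affected by treatment. The protocol does not say whether thrombosed pre-dialysis patients count as failures or drop out, and the two choices bias the result in opposite directions. At stake is the main secondary outcome, which shows whether better early patency yields a usable access. The six-week patency outcome is not touched.

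The power statement has a related gap. It rests on all 1,284 patients, although 4.1 and 4.5 foresee patients without this outcome. The comparison of deaths has a milder version of the problem, because time in the study also depends on thrombosis.

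**Working it through.** **Inputs from Protocol 8.1 and 2.2.** Two-sided alpha 0.05, stated for the primary outcome ("with 85% power and a 2 sided-alpha level of 0.05, 1284 patients are required (642 in each treatment group") and taken to hold here; equal allocation ("Randomization will be on a 1:1 active drug:placebo allocation"). Placebo thrombosis: "fistula thrombosis at 6 weeks (primary outcome) will occur in 25% of patients treated with placebo"; a 30% reduction gives 17.5%. Placebo suitability failure 40%; a 20% reduction gives 32%. Loss 5%, drop-in 3%, drop-out 3%.

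**Power formula.** Power = Φ[(|p1 − p2| − 1.96·SE0)/SE1], with SE0 from the pooled and SE1 from the separate proportions.

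**Step 1: reproduce the stated 80%.** Mixing 3% of each arm:
- placebo 0.97·40% + 0.03·32% = 39.76%
- clopidogrel 0.97·32% + 0.03·40% = 32.24%

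With 642 per arm, power is 80.2%. After 5% loss (642·0.95 = 609.9 per arm) it is 78.2%. Without mixing the figures are 84.8% and 83.0%. The stated figure reproduces. The same mixing applied to the primary outcome gives 604 per arm, and 604/0.95·1.027·2 = 1,306, within 2% of 1,284.

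**Step 2: neutral non-ascertainment.** A further share is missing for reasons unrelated to outcome, after the 5% loss:

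| Further share missing | n per arm | Power with mixing | Power without mixing |
|---|---|---|---|
| 5% | 579 | 76.1% | 81.1% |
| 10% | 549 | 73.8% | 78.9% |
| 20% | 488 | 68.7% | 74.1% |
| 30% | 427 | 62.9% | 68.3% |

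80% power needs 639 per arm with mixing, so there is no room after loss. Without mixing it needs 564, which leaves 1 − 564/609.9 = 7.5%.

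**Step 3: outcome-dependent inclusion.** Let t be the thrombosis rate, F the true failure rate, f the pre-dialysis share, u the share of these who never start, and g = f·u. The protocol gives neither f nor u; the base case assumes f = 0.5 and u = 0.2, so g = 0.1. Further assumptions: every thrombosis is unrestored and, in pre-dialysis patients, precedes dialysis start; starting dialysis is unrelated to fistula outcome; 609.9 per arm; no mixing. With everyone ascertained the difference is 8.0 points and power 83.0%.

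*(a) Thrombosed patients all count as failures.* Denominator share D = t + (1−t)(1−g); observed failure = 1 − (1−F)(1−g)/D.
- Placebo: D = 0.25 + 0.75·0.9 = 0.925; failure 1 − 0.54/0.925 = 41.6%.
- Clopidogrel: D = 0.175 + 0.825·0.9 = 0.9175; failure 1 − 0.612/0.9175 = 33.3%.
- Difference 8.3 points, power 82.3%.
- No true effect on suitability (40% in both arms) but fewer thromboses on clopidogrel: 41.6% vs 1 − 0.54/0.9175 = 41.1%, a spurious 0.5 points in favour of clopidogrel.
- Over f = 0.3-0.7 and u = 0.1-0.3, the spurious difference is 0.1-1.1 points and power at the design effect 81-83%. At g = 0.2, the chance of a false finding for clopidogrel is about 5.1% instead of 2.5%.

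*(b) Thrombosed pre-dialysis patients are dropped.* D = t(1−f) + (1−t)(1−g).
- Placebo: D = 0.125 + 0.675 = 0.80; failure 1 − 0.54/0.80 = 32.5%.
- Clopidogrel: D = 0.0875 + 0.7425 = 0.83; failure 1 − 0.612/0.83 = 26.3%.
- Difference 6.2 points, power 58%. With f = 0.3 it is 7.1 points and 70%; with f = 0.7 it is 5.1 points and 42%.
- No true effect: 32.5% vs 1 − 0.54/0.83 = 34.9%, an apparent harm of 2.4 points.

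**Step 4: time at risk for death.** Assume 45 days in the study after thrombosis and 165 days otherwise. The mean is 0.75·165 + 0.25·45 = 135 days on placebo and 0.825·165 + 0.175·45 = 144 on clopidogrel, about 7% longer.

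**The case against.** The strongest reply is that the text points to one reading. Section 4.5 words the non-ascertainment rule by the end of the study period and applies it to patients still followed then; unrestored thrombosis has its own paragraph. Sections 4.4.4 and 4.4.6 continue follow-up to the suitability assessment only when patency is restored, and 7.1 requires at least four weeks of use. A lost fistula is thus naturally a failure, and under case (a) little goes wrong. Denominators are also commonly left to an analysis plan, which is not at hand.

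Most of this stands. It makes case (a) the likelier one and the harm small. It does not remove the point: an analysis plan can class a lost fistula as a failure, but cannot recover dialysis start dates that the protocol stops collecting.

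Four stronger inferences are tempting and not supported:
- *The 80% power is not delivered.* The figure reproduces. A shortfall depends on a never-start share that the protocol does not give.
- *The bias must run against clopidogrel.* That holds only if thrombosed patients are dropped; on the natural reading it runs the other way.
- *Deaths are recorded only during participation.* Sections 4.5 and 5.4 plan national mortality data afterwards. What stays open is which data and horizon the comparison uses.
- *Early stopping undercuts the secondary power.* Section 8.1 says the figure is for a fixed design, so that condition is disclosed.

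**Conclusion.** The point holds in limited form. Inclusion in the suitability comparison depends on thrombosis under either reading, because dialysis start is not followed after an unrestored loss.

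On the natural reading the effect is small: about 0.1 to 1.1 points toward clopidogrel when suitability is truly equal, with power nearly unchanged. On the drop-out reading it is material and in the opposite direction: 6.2 rather than 8.0 points and 58% rather than 83% power in the base case. These sizes rest on assumed pre-dialysis and never-start shares and on the simplifications in step 3.

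The stated power is correct for full ascertainment but has little or no reserve: with drop-in, drop-out and 5% loss, a further neutral 10% or 20% without an outcome leaves about 74% or 69%. The matter should be corrected, since it concerns a main secondary outcome and uncollected dates may not be recoverable later.

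**What to change.** 1. State in 7.1 that permanent loss of the fistula is a suitability failure.
2. Apply one inclusion rule regardless of thrombosis: on dialysis at randomization, or dialysis started by a common cut-off. Keep collecting the dialysis start date for thrombosed pre-dialysis patients by continued contact. The linkage in 4.5, 5.4 and 10.2 names hospitalization, procedures and death, not dialysis start, so it should not be relied on for this date.
3. Restate the secondary power in 8.1 for the number of patients expected to be ascertainable, and give the assumed share.
4. Compare deaths to a common fixed day from randomization, using the mortality data already planned.

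The cost is one date per thrombosed pre-dialysis patient, a few sentences of protocol text, and a slightly less favourable stated power.
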